#### CONFIDENTIAL

• mg Q2W in patients who weigh  $\geq$  30 kg to <60 kg

NOTE: In Part A, patients will receive dupilumab injections at the frequency of Q2W or Q4W with matching placebo alternating with dupilumab doses so the injection frequency will be Q2W for both groups for regimen-blinding purposes per treatment assignment in Part A.

- Placebo for Part A: Dose matching placebo Q2W or alternating with dupilumab Q4W so the frequency will be Q2W for both groups for regimen-blinding purposes in Part A.
- See Figure 3: Weight-Tiered Dosing Regimens of Study Drug Part A.
- Part B: 36-Week Extended Active Treatment Period: Part B is the extended active treatment portion of the study. All patients (Part A active and placebo) will receive dupilumab based on body weight at visit 8 (week 16, end of double-blinded treatment period or start of extended treatment period) per the higher and lower exposure group to which they were assigned at randomization. If weight tier has increased at visit 12 / week 32, patients will be re-assigned to an extended active treatment regimen based on weight tiered dosing regimens below.

Higher exposure dupilumab regimens (Part B):

- mg Q2W in patients who weigh  $\geq$ 5 kg to <15 kg
- mg Q2W in patients who weigh  $\geq 15$  kg to <30 kg
- mg Q2W in patients who weigh  $\geq$ 30 kg to <60 kg
- mg QW in patients who weigh  $\geq 60$  kg

Lower exposure dupilumab regimens (Part B):

- mg Q4W in patients who weigh  $\geq$ 5 kg to <15 kg
- mg Q4W in patients who weigh  $\geq 15$  kg to <30 kg
- mg Q2W in patients who weigh  $\geq$ 30 kg to <60 kg
- mg Q2W in patients who weigh  $\geq 60$  kg

NOTE: In Part B, study drug or matching placebo will be administered Q2W for all patients in <60 kg weight-groups and QW for all patients in  $\geq$ 60 kg weight-groups. Patients will receive alternating doses of dupilumab or placebo Q2W for patients <60 kg assigned to Q4W regimens or QW for patients  $\geq$ 60 kg assigned to Q2W regimens for regimen-blinding purposes

Placebo for Part B: Dose matching placebo alternating with dupilumab Q2W or Q4W so the frequency will be Q2W for the weight-based groups <60kg and QW for the weight-based group of ≥60 kg for regimen-blinding purposes in Part B.

See Figure 4: Part B Weight-Tiered Dosing Regimens of Study Drug.

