Medical History											Х
Treatment:											
Administer Study Drug 4a, 4b	Х	Х	Х	Х	Х	Х	Х	Х	Х	Х	
Con Meds/Procedures	Х	Х	Х	Х	Х	Х	Х	Х	Х	Х	
Efficacy:											
Age in months	Х	Х	Х	Х	Х	Х	Х	Х	Х	Х	
Weight, Height (or length for patients <2 years of age) 	X 4b	Х	X	Х	X 4b	X	Х	Х	Х	Х	
Pediatric EoE Sign/Symptom Questionnaire:  Patient version (PESQ-P) Corregiver version	(Daily Diary)									>	
(PESQ-C)											
Pediatric EoE Impact Scale:  Patient version (PEIS-P) Caregiver version (PEIS-C)	Х				X					Х	

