- 15. The Pediatric Eosinophilic Esophagitis Symptom Score (PEESS) version 2.0 will be completed by caregivers of patients ≥1 to <12 years of age (determined at the time of screening visit 1).
- 16. Exit interviews will be conducted by a trained interviewer by telephone within 14 days of completing week 16/visit 8. These interviews will be completed with caregivers. Patients aged ≥8 to <12 years old (determined at the time of screening visit 1) may also join a portion of the exit interview.

#### 9.1.1.2. Footnotes for Table 2

- 1. This visit is the same as the week 16 visit for the double-blind study portion (Table 1), and all other assessments indicated for week 16 (Table 1) should be performed. Endoscopy with biopsies at visit 8/week 16 must be completed prior to administration of study drug for Part B Extended Active Treatment.
- 2. Study assessments will be performed, and blood samples will be collected prior to administration of study drug. In the event of suspected SAEs, such as anaphylaxis or hypersensitivity, functional dupilumab PK sample and anti-dupilumab antibody sample may be collected at or near the event.
- 3. In addition to predose assessments, AEs and vital signs (body temperature, blood pressure, respiratory rate, and heart rate) will be assessed at 30 minutes (±10 minutes) post-dose.
- 4. 4a. Study drug administration will continue through week 50.

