4b. Weight assessed at visit 8 / week 16 and visit 12 / week 32 will be used to determine weight-tiered dose for the 36-week extended active treatment period. If weight has increased at visit 12 such that the patient meets a larger weight tier, weight-tiered dosing will be re-assigned according to the patient's weight at this visit. If weight is the same or decreased at visit 12, then weight-tiered dosing will remain as originally assigned at visit 8 / week 16. The patient will remain within the original exposure dosing assignment (higher exposure group or lower exposure group). On scheduled in-clinic study visit days, study drug will be administered in the clinic (by the patient, site staff, or caregiver). Study drug administered at the study sites by site staff will be performed only by injection personnel who will not perform any clinical assessment/procedures. Study drug will be provided for those scheduled doses to be administered at home before the next in-clinic visit. Parents (or caregivers) will return the study kit box (for prefilled syringes) at each subsequent inclinic visit. Study drug administration that occurs in clinic should occur per the Schedule of Events table. Parents (or caregivers) who prefer to have the clinic staff administer study drug may choose to have injections administered in the clinic.

- 5. The PESQ-P will be completed daily by patients ≥8 to <12 years of age (determined at the time of screening visit 1) just before going to bed for the night. The PESQ-C will be completed daily by caregivers of patients ≥1 to <12 years of age (determined at the time of screening visit 1) after the patients go to bed for the night. The PESQ-P and PESQ-C will be completed via an electronic diary (diary) and site personnel should conduct regular checks of patient and caregiver diary compliance. The PEIS-P and PEIS-C will be completed during site visits as indicated in the Schedule of Events table by the patients and caregivers, respectively.

- 6. The GIS-P, GIS-C, GIS-Clin and the GIC-P, GIC-C, and GIC-Clin will be completed during site visits by patients (≥8 to <12 years of age determined at the time of screening visit 1), caregivers (of patients ≥1 to <12 years of age determined at the time of screening visit 1), and study investigator/clinician, respectively.

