- The GIS-P, GIS-C, GIS-Clin and the GIC-P, GIC-C, and GIC-Clin will be completed during site visits as indicated by patients (≥8 to <12 years of age determined at the time of screening visit 1), caregivers (of patients ≥1 to <12 years of age determined at the time of screening visit 1), and study investigator/clinician, respectively.
- 4. EoE-EREFS imaging will be analyzed and scored by a central reading center. Minor esophageal features will be assessed by the investigator.

4a. For patients who receive rescue treatment, endoscopy/imaging for EoE-EREFS/biopsy procedures will be performed prior to initiation of rescue treatment. Patients undergoing endoscopy/biopsy prior to rescue will not undergo the any future scheduled endoscopy/biopsy (weeks 16, 52, 100 and/or 160).

4b. Endoscopy/imaging for EoE-EREFS/biopsy will be performed only if the unscheduled visit is for the purpose of administering rescue therapy.

- 5. Urinalysis is only required for patients aged  $\geq 6$  years
- 6. The Pediatric Eosinophilic Esophagitis Symptom Score (PEESS) version 2.0 will only be completed by caregivers of patients >1 to <12 years of age (determined at the time of screening visit 1) at an early termination and/or unscheduled visit before rescue visit(s).

## 9.1.1.4. Footnotes for Table 4

- 1. This visit is the same as the week 52 visit for the extended active treatment period for those patients entering Part C immediately after Part B (Table 2) or during the Safety follow-up period, and all other assessments indicated for week 52 (Table 2) should be performed prior to this portion of the visit.
- Endoscopy with biopsies at visit 17/week 52 must be completed prior to administration of study drug for Part C - Open-Label Extension Period. Study drug administration is based on weight-tier (Section 8.1 Investigational and Reference Treatments) Weight must be collected at all in-clinic visits. Dose is assigned to match weight group for baseline for Part C (Week 52) and re-assigned after week 52 only if weight increases.
- 3. The PEIS-P and PEIS-C will be completed during site visits as indicated in the Schedule of Events table by the patients and caregivers, respectively.
- The GIS-P, GIS-C, and GIS-Clin will be completed by patients during site visits (>8 to <12 years of age determined at the time of screening visit 1), caregivers (of patients ≥1 to <12 years of age determined at the time of screening visit 1), and study investigator/clinician, respectively.

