## 11.4.5.3. Treatment Exposure

The duration of exposure during part A, part B and part C of the study will be presented by treatment group and calculated as:

(Date of last study drug injection in the specific study part – date of first study drug injection in the specific study part) + 14 days

Number (%) of patients exposed to study drug during each study part and cumulatively across study parts will be presented by specific time periods for each treatment group. The time periods of interest will be specified in the SAP.

In addition, duration of exposure during the study will be summarized for each treatment group using number of patients, means, standard deviation, minimums, medians, and maximums.

A summary of the number of doses by treatment group will be provided.

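### Table 2 marks study drug at week 52 while its own footnote ends dosing at week 50, so visit 17 dosing is contradictory for children who stop after Part B and not assigned to a part for those who continue

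*Protocol*

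**What the plan says.** The study-drug row of Table 2 ("Administer Study Drug 4a, 4b") has a mark in each of the ten visit columns from visit 8/week 16 to visit 17/week 52; only the Re-Entry column is blank. Two footnotes hang on that row (Section 9.1.1.2):

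- Footnote 4a: "Study drug administration will continue through week 50".
- Footnote 4b: "Study drug administration that occurs in clinic should occur per the Schedule of Events table".

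Visit 17 is also the first column of Table 4. Footnote 12 to Table 2 says that children entering the extension have further week 52 events listed in Table 4. Footnote 1 to Table 4 (Section 9.1.1.4) says that visit 17 is the same visit and that the other week 52 assessments of Table 2 come before the Part C portion. The next footnote adds: "Endoscopy with biopsies at visit 17/week 52 must be completed prior to administration of study drug for Part C".

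Section 8.1 heads the period "Part B: 36-Week Extended Active Treatment Period" and sets the injection frequency: "study drug or matching placebo will be administered Q2W for all patients in <60 kg weight-groups", with weekly injections at 60 kg or above. Section 11.4.5.3 computes exposure per study part as the last injection date minus the "date of first study drug injection in the specific study part) + 14 days".

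Table 1 treats the earlier transition differently. Its "Administer Study Drug" row is blank at visit 8, the end of Part A, and the week 16 dose appears only in Table 2.

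**The concern.** A mark and its own footnote give opposite instructions for the same day, and footnote 4b, which might have settled the matter, points back to the mark. No passage says whether the visit 17 mark is a Part B dose, the first Part C dose or a leftover, and none limits it to children who enter Part C.

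For a child who leaves after Part B, the question is whether one more blinded injection is given just before follow-up. Several rules count from the last dose: the study-day entry for the end-of-study visit in Table 4 (84 days), contraception (12 weeks, exclusion criterion 31), pregnancy reporting (12 weeks, Section 10.1.3) and the live-vaccine restriction (3 months, Section 8.10.3). All of them move with the answer.

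For a child who continues directly, the question is accounting. Part B kits are blinded, Part C drug is labeled as dupilumab (Section 8.7), and exposure, compliance and adverse events are summarized per part. If the week 52 injection is not assigned to a part, the summaries on both sides of the boundary depend on an unstated choice.

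**Working it through.** **Is week 52 really marked?** Table 2 has ten visit columns (visits 8 to 17) plus Re-Entry. The study-drug row has ten marks. The concomitant-medication and adverse-event rows also have ten, and the vital-signs row has eleven, including Re-Entry. The rows line up, so the tenth study-drug mark belongs to visit 17/week 52.

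**Inputs.** First Part B injection: week 16, day 16 × 7 + 1 = 113 (Table 2). Last Part B injection: week 50, day 50 × 7 + 1 = 351 (footnote 4a), or week 52, day 52 × 7 + 1 = 365 (table mark). Stated length of Part B: 36 weeks (Section 8.1).

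**Formulas.** Exposure = last day − first day + 14 (Section 11.4.5.3). Every-2-week injections = (last week − 16)/2 + 1. Weekly injections = (last week − 16) + 1.

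**The formula on Part A first.** With every-2-week dosing from week 0 and no dose marked at week 16, the last injection is at week 14: 14 × 7 + 14 = 112 days = 16.0 weeks, the stated length of Part A.

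**Part B under each instruction:**

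| Last Part B injection | Exposure | Every-2-week injections | Weekly injections | Last dose + 12 weeks |
|---|---|---|---|---|
| Week 50 (footnote 4a) | 351 − 113 + 14 = 252 days = 36.0 weeks | 34/2 + 1 = 18 | 34 + 1 = 35 | week 62 |
| Week 52 (table mark) | 365 − 113 + 14 = 266 days = 38.0 weeks | 36/2 + 1 = 19 | 36 + 1 = 37 | week 64 |

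The weekly count of 37 assumes that dosing also continues at week 51.

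Footnote 4a reproduces the stated 36 weeks and the table mark does not. That shows the passages disagree with each other and with the period length; it does not settle which dosing rule the sponsor intends.

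**Would the extra injection contain drug?** In the every-2-week active regimens, yes. In the every-4-week regimens, if active doses run from week 16 (an assumption), week 52 falls on an active slot, because 52 − 16 = 36 is a multiple of 4. Active doses would then number 9 through week 48, or 10 with week 52.

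**Direct continuers.** Footnote 4a closes Part B dosing at week 50, footnote 1 to Table 4 makes visit 17 a shared visit, and the following Table 4 footnote refers to Part C drug after the week 52 endoscopy. Together these point to one injection at visit 17, belonging to Part C. The Table 2 mark, read alone, would place an injection that day in Part B.

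**The case against.** The strongest reply is that the text is coherent for most children and the rest is clerical. For a child going straight into Part C this largely stands: a single Part C dose at visit 17 is the natural reading, and only its labeling by part is unclear. The reply does not help the child who stops after Part B, for whom the mark and the footnote cannot both be followed.

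Four stronger inferences are tempting, and the documents do not support them.

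- *Two doses on one day.* A reader might infer a Part B and a Part C injection at visit 17, because footnote 12 describes the Table 4 events as coming on top of Table 2. That wording is general, footnote 1 to Table 4 speaks of assessments rather than injections, and the two supplies are labeled differently. No passage calls for two doses.
- *Every child who reaches week 52 is affected.* Re-entry patients completed their end-of-study visit before Amendment 4, and some others were already in follow-up (Section 6.1). Their Part B dosing was over before this version applied, and the Re-Entry cell of the study-drug row is blank.
- *Compliance shifts by about 5 points.* The figures 18/19 = 94.7% and 19/18 = 105.6% arise only if a child is dosed under one instruction and scored under the other. Scored consistently, both readings give 100% (18/18 or 19/19). Section 11.4.5.4 divides by the planned injections in the exposure period and states no count that is wrong.
- *The efficacy results are at risk.* The primary analysis is at week 16. Part B and Part C are summarized descriptively, and week 52 assessments and samples are to precede dosing.

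**Conclusion.** The contradiction stands. It sits within one table row and that row's own footnotes, and it is an operational dosing instruction rather than detail that could wait for an analysis plan.

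For children who finish Part B under this version and do not enter Part C, the protocol both schedules and excludes a blinded week 52 dose. The difference is one every-2-week injection, two weeks on the last-dose date and on what is counted from it, and 14 days of Part B exposure (252 against 266). The number of such children is not given in the protocol. For direct continuers the defect is smaller: one injection whose study part is not stated, which affects exposure, compliance and adverse event attribution by part.

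The exposure figures assume a first Part B dose at week 16 and no missed or delayed injections. The consequences are for conduct and descriptive summaries, with no effect on the week 16 inference. It should be corrected, but it is a modest point.

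**What to change.** Reconcile three places so that only one governs study drug at visit 17: the visit 17 mark in the Table 2 study-drug row, footnote 4a, and the Table 4 study-drug row with its footnotes 1 and 2. State the rule separately for children who enter Part C and for those who do not, and say to which study part any injection given at visit 17 belongs for exposure, compliance and adverse event summaries. The choice of dosing rule is the sponsor's; the request is only that the passages agree with each other and with the stated length of Part B.

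The cost is a wording change in one table row, its footnote and one cross-reference, plus a memo to sites. No sample size, endpoint or analysis method changes.

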## 9.1.2. Early Termination Visit

Patients who are withdrawn from the study will be asked to return to the clinic for an early termination visit consisting of the assessments described in Table 3.

#### 9.1.3. Unscheduled Visits

All attempts should be made to keep patients on the study schedule. Unscheduled visits may be necessary to repeat testing following abnormal laboratory results, for follow-up of AEs, or for any other reason, as warranted.

#### 9.1.4. **Re-Entry Visit**

Patients who have completed their end of study visit prior to entering the open-label extension period are eligible for re-entry to the study for the open-label extension period. The following study procedures are required at a Re-Entry Visit:

- Part C re-entry criteria (Section 7.2.2.2)
- Informed consent
- Updates for all relevant medical history and prior and concomitant medications/procedures
- Physical Examination
- Age, weight, height (length for patients <2 years of age)

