#### Figure 1: Study Flow Diagram

After patients and their legal parents/legal guardians provide informed assent (as appropriate) and informed consent, patients will be assessed for study eligibility.

Patients who have completed their end of study (EOS) visit prior to amendment 4 will be reevaluated for eligibility at a Re-Entry visit for participation in the open-label extension period (Part C) and Safety Follow-up period (see Section 7.2.2.3). Patients who have entered the safety followup period after completing Part B at the time of amendment 4 approval may immediately enter the open-label extension (Part C) without being required to complete an EOS visit prior to entering Part C.

Patients are required to have a documented diagnosis of EoE which may be established either by a prior historical biopsy, as demonstrated by intraepithelial eosinophilic infiltration (peak eosinophils/high power field  $\geq$ 15 eos/hpf) (400×) from at least 1 esophageal region and performed after at least 8 weeks of treatment with an approved PPI regimen, or by biopsies performed after approximately 8 weeks of PPI treatment initiated prior to screening or during the screening period, which demonstrates  $\geq$ 15 eos/hpf) (400×) from at least 2 of the 3 esophageal regions (proximal, mid, and distal); if the PPI regimen is stopped, biopsies must occur within 2 weeks of stopping the PPI. See Figure 2 for endoscopy/biopsy procedure flow chart.

Regeneron Pharmaceuticals, Inc.

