- 16. Planned or anticipated use of any prohibited medications and procedures during the study
- 17. Planned or anticipated major surgical procedure during the study
- 18. Treatment with a live (attenuated) vaccine within 4 weeks before the baseline visit

NOTE: For patients who have vaccination with live, attenuated vaccines planned during the course of the study (based on national vaccination schedule/local guidelines), it will be determined, after consultation with a pediatrician, whether the administration of vaccine can be postponed until after the end of study, or preponed to before the start of the study, without compromising the health of the patient:

- Patients for whom administration of live (attenuated) vaccine can be safely postponed would be eligible to enroll into the study
- Patients who have their vaccination preponed can enroll in the study only after at least 4 weeks following administration of the vaccine
- 19. Active parasitic infection or suspected parasitic infection, unless clinical and (if necessary) laboratory assessments have ruled out active infection before randomization
- 20. Chronic or acute infection requiring treatment with systemic antibiotics, antivirals, or antifungals within 2 weeks before baseline visit

NOTE: Patients may be re-screened after the infection resolves

21. Known or suspected immunodeficiency disorder, including history of invasive opportunistic infections (eg, tuberculosis [TB], non-tuberculous mycobacterial infections, histoplasmosis, listeriosis, coccidioidomycosis, pneumocystosis, aspergillosis) despite infection resolution, or otherwise recurrent infections of abnormal frequency, or prolonged infections suggesting an immune-compromised status, as judged by the investigator

NOTE: Tuberculosis testing will be performed on a country-by-country basis according to local guidelines if required by regulatory authorities or ethics committees (ECs).

- 22. Known history of human immunodeficiency virus (HIV) infection or positivity for Hepatitis B or Hepatitis C antigens
- 23. On current treatment for hepatic disease including but not limited to acute or chronic hepatitis, cirrhosis, or hepatic failure, or has evidence of liver disease as indicated by persistent (confirmed by repeated tests ≥2 weeks apart) elevated transaminases (alanine aminotransferase [ALT] and/or aspartate aminotransferase [AST]) more than 3 times the upper limit of normal [ULN] during the screening period)

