# 7.2.2.2. Exclusion Criteria for Part B – Extended Active Treatment (and also for Entry into Part C for Patients with Uninterrupted Participation in the Study)

- 1. Patients who, during the double-blind treatment period (for entry into the extended active period) or during the extended active treatment period (for entry into the open-label extension period), developed an SAE and/or AE deemed related to study drug and which led to discontinuation of investigational product (patients who are prematurely discontinued from study drug due to lack of efficacy are eligible to enter Part B and/or Part C)
- 2. Patients who, during the double-blind treatment period (for entry into the extended active period), or extended active treatment period (for entry into the open-label extension period) were prematurely withdrawn because of a protocol violation, poor compliance, or inability to complete required study assessments
- 3. Patients who did not undergo endoscopy with biopsies at week 16 and/or week 52 or prior to receiving rescue treatment

Note: If the endoscopy with biopsies could not occur due to COVID-19 restrictions and rescue treatment was needed to be initiated without delay, these patients will be eligible to participate in Part C.

4. Female patients who experience menarche and who are unwilling to follow the precautions for WOCBP

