# 7.2.2.3. Exclusion Criteria for Patients Re-Entering the Study (for Entry into Part C for Patients Who Have Completed Their EOS Visit Prior to Amendment 4)

A patient who meets any of the following criteria will not be permitted to re-enter the study:

1. Patients who are ≥12 years old, weigh ≥40 kg (or minimum weight for which dupilumab is approved for EoE), and dupilumab is commercially available for the treatment of EoE in their country.

- 2. Patients who, during their previous participation in this clinical trial, developed an SAE and/or AE deemed related to dupilumab, which in the opinion of the investigator or of the medical monitor could indicate that continued treatment with dupilumab may present an unreasonable risk for the patient.
- 3. Patients who did not undergo endoscopy with biopsies at week 16 and/or week 52 or prior to receiving rescue treatment.

Note: If the endoscopy with biopsies could not occur due to COVID-19 restrictions and rescue treatment was needed to be initiated without delay, these patients will be eligible to participate in Part C.

- 4. Patients who became pregnant during their previous participation in this dupilumab clinical trial.
- 5. Patients who, during their previous participation in this trial, were prematurely withdrawn because of a protocol violation, poor compliance, or inability to complete required study assessments.
- 6. Known history of HIV infection or HIV seropositivity.
- 7. Known history of positive HBsAg, HBcAb, or hepatitis C antibody.

NOTE: Patients who are HBsAg negative and HBsAb positive are considered immune after a natural infection has cleared or they have been vaccinated against hepatitis B. Therefore, they are acceptable for the study.

- 8. Treatment with an investigational drug (other than dupilumab) within 2 months or within 5 half-lives (if known), whichever is longer, prior to the re-entry visit
- Treatment with systemic immunosuppressant/immunomodulating drugs, including but not limited to mepolizumab, omalizumab, cyclosporine, mycophenolate-mofetil, interferongamma (IFN-γ), Janus kinase inhibitors, azathioprine, and methotrexate within 3 months prior to re-entry visit
- 10. Treatment with a live (attenuated) vaccine within 4 weeks before the re-entry visit.
- 11. Chronic or acute infection requiring treatment with systemic antibiotics, antivirals, or antifungals within 2 weeks before re-entry visit
- 12. Pregnant or breastfeeding females

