- 13. Females unwilling to use adequate birth control, if of reproductive potential and sexually active (see Exclusion Criterion 31 above for applicable definitions).
- 14. Any other medical or psychological condition that, in the opinion of the investigator, may suggest a new and/or insufficiently understood disease, may present an unreasonable risk to the patient as a result of his/her participation in the trial, may make the patient's participation unreliable, or may interfere with study assessments. The specific justification for patients excluded under this criterion will be noted in the source documents.

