#### 8.10.3. Restricted Medications and Procedures during the Follow-Up Period

Patients may receive the prohibited medications/procedures listed in Section 8.10.1 as needed during the follow-up period, with the exception of live (attenuated) vaccine, which should not be used within 3 months after the last dose of study drug. Investigators are advised to prescribe prohibited medications/procedures judiciously, only when they are absolutely required for the appropriate management of study patients.

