7. Endoscopy/imaging for EoE-EREFS/biopsy procedures should be performed after all other efficacy and safety assessments. Minor esophageal features will be assessed by the investigator.

7a. For patients who receive rescue treatment, endoscopy/EoE-EREFS/biopsy procedures will be performed prior to initiation of rescue treatment. Patients undergoing endoscopy/biopsy prior to rescue will not undergo the scheduled endoscopy/biopsy at weeks 16 and 52.

- 8. In addition to the predose assessments, AEs and vital signs (body temperature, blood pressure, respiratory rate, and heart rate) will be assessed at 30 minutes (±10 minutes) post-dose at visit 8.
- 9. In case of a positive urine pregnancy test, the study treatment will be withheld and a serum pregnancy test to confirm the pregnancy should be performed as soon as possible. A confirmed pregnancy will lead to study drug discontinuation in all cases.
- 10. Urinalysis is only required for patients aged  $\geq 6$  years.
- 11. The Pediatric Eosinophilic Esophagitis Symptom Score (PEESS) version 2.0 will be completed by caregivers of patients >1 to <12 years of age (determined at the time of screening visit 1).
- 12. Assessments indicated for this week 52 (end of extended active treatment) visit should be performed for all patients. For patients who will enter the open-label extension period, there are additional events listed for the week 52 visit in Table 4.
- 13. For a complete list of procedures to be performed for Re-Entry patients, please see Table 4.

#### 9.1.1.3. Footnotes for Table 3

- 1. Patients who are withdrawn from study drug will be asked to complete the 12-week followup period and the end of study visit.
- 2. The PESQ-P will be completed daily by patients ≥8 to <12 years of age (determined at the time of screening visit 1) just before going to bed for the night. The PESQ-C will be completed daily by caregivers of patients ≥1 to <12 years of age (determined at the time of screening visit 1) after the patients go to bed for the night. The PESQ-P and PESQ-C will be completed via an electronic diary (diary) and site personnel should conduct regular checks of patient and caregiver diary compliance. The PEIS-P and PEIS-C will be completed during site visits as indicated in the Schedule of Events table by the patients and caregivers, respectively.

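### Section 9.1.4 points re-entry patients to the wrong exclusion list: Section 7.2.2.2 (4 criteria, uninterrupted participation) instead of Section 7.2.2.3 (14 criteria)

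*Protocol*

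**What the plan says.** Four places in the protocol bear on which list applies at re-entry.

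- **Section 9.1.4, Re-Entry Visit.** It covers patients who completed their EOS visit before entering the open-label extension. Its first required item is "Part C re-entry criteria (Section 7.2.2.2". It also requires informed consent, updates of medical history and of prior and concomitant medications and procedures, a physical examination, and age, weight and height.
- **Section 7.2.2.2.** This is the Part B exclusion list. Its heading extends it to Part C as follows: "and also for Entry into Part C for Patients with Uninterrupted Participation in the Study". It has 4 criteria.
- **Section 7.2.2.3.** Its heading assigns it to patients who completed EOS before Amendment 4 and re-enter for Part C. It has 14 criteria, among them "Treatment with a live (attenuated) vaccine within 4 weeks before the re-entry visit" (criterion 10) and a general safety criterion that begins "Any other medical or psychological condition that, in the opinion of the investigator, may suggest a new and/or insufficiently understood disease" (criterion 14). Its opening line bars re-entry for anyone who meets any of them.
- **Section 6.1.** It says that patients who completed EOS before Amendment 4 are re-evaluated at a Re-Entry visit for Part C "and Safety Follow-up period (see Section 7.2.2.3".

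The Re-Entry column of Table 2 marks an inclusion/exclusion check but names no section.

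**The concern.** Two operative sections name different exclusion lists for one visit. The one in the visit-procedures section is the list that, by its own heading, does not apply to these patients.

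What is at stake is what may have happened while the child was off study. Live vaccination shows it most clearly. The note to Part A exclusion 18 asks "whether the administration of vaccine can be postponed until after the end of study", so some children may have deferred a vaccine to that point. Section 8.10.3 relaxes the medication restrictions in follow-up, "with the exception of live (attenuated) vaccine, which should not be used within 3 months after the last dose of study drug". A child who has left the study and is past that interval is free to receive the deferred vaccine. If the child then seeks re-entry, criterion 10 of Section 7.2.2.3 is the only stated interval (4 weeks) between a live vaccine and the restart of dupilumab. Section 7.2.2.2 has no such criterion. It also lacks the washouts for another investigational drug (criterion 8) and for systemic immunosuppressants (criterion 9).

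**Working it through.** No sample size, power or error rate enters this point. The check sets the two lists side by side and counts.

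**Step 1: match each criterion of 7.2.2.3 to 7.2.2.2.**

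| 7.2.2.3 criterion | Counterpart in 7.2.2.2 | Back-up elsewhere |
|---|---|---|
| 1 Age, weight, commercial availability | None | Partly: Part C stop rule in 8.1 |
| 2 Related SAE/AE suggesting unreasonable risk | No. 1, narrower | n/a |
| 3 No endoscopy with biopsies | No. 3 | n/a |
| 4 Pregnancy during earlier participation | None | Partly: pregnancy stop rule in 8.4.2.1 |
| 5 Withdrawn for violation or poor compliance | No. 2 | n/a |
| 6 HIV | None | Partly: Part A exclusion 22 |
| 7 Hepatitis B or C | None | Partly: Part A exclusion 22 |
| 8 Investigational drug washout | None | None |
| 9 Immunosuppressant washout | None | None |
| 10 Live vaccine washout | None | None |
| 11 Infection on systemic treatment | None | Partly: 8.4.2.2 |
| 12 Pregnant or breastfeeding | None | Partly: 8.4.2.1 and urine test at the visit |
| 13 Contraception | No. 4, worded differently | n/a |
| 14 General safety criterion | None | Partly: 8.4.2.2 |

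**Step 2: count.**

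- Criteria with no counterpart in the cited list: 14 − 4 (nos. 2, 3, 5, 13) = 10.
- Of these, criteria 1, 4, 6, 7 and 12 are at least partly backed up elsewhere: 10 − 5 = 5 left (8, 9, 10, 11, 14).
- Section 8.4.2.2 suspends dosing for an infection that needs parenteral anti-infectives, or oral ones for longer than 2 weeks, and for intercurrent illness that the investigator judges an unreasonable risk. That partly covers 11 and 14, but it sets no look-back at re-entry: 5 − 2 = 3 left (8, 9, 10).

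**Step 3: check that 8, 9 and 10 really have no back-up.** The Part A versions (exclusions 14, 13 and 18) are timed to the original screening or baseline. The prohibited-medication list in Section 8.10.1 is introduced as running through week 52 and sets no washout before a restart.

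**Step 4: compare strictness where a counterpart exists.** For Part C entry, criterion 1 of 7.2.2.2 needs a related event that led to discontinuation of study drug during the extended active period. Criterion 2 of 7.2.2.3 covers any related event in the whole earlier participation that the investigator or medical monitor thinks could signal unreasonable risk with continued treatment. The cited list is narrower here too.

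**The case against.** The strongest reply is that the error is one digit in a procedures list and that the protocol corrects it nearly everywhere else. Section 7.2.2.3 binds by its own words, and a wrong pointer does not cancel that. A site that turns to 7.2.2.2 meets a heading that excludes its patient, and the next list is headed for re-entering patients. Section 6.1 gives the right reference. Section 9.1.4 itself also requires updated medical history and medications, so interim drugs, vaccines and infections should be recorded at the visit.

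All of this stands, and it limits the consequence. A reader might infer that the missing criteria would go wholly unchecked. The documents do not support that, because the information is gathered and the correct list remains in force. What a site following the pointer would lose is the formal threshold, for example 4 weeks since a live vaccine.

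Three other stronger readings are tempting.

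- **That all five criteria left after the first count are unprotected.** If the pregnancy stop rule counts as partial back-up for criteria 4 and 12, then Section 8.4.2.2 must count for 11 and 14. That leaves three.
- **That the vaccine bar can be dated to so many days after EOS.** This would need an assumed gap between last dose and EOS, and the point does not need it. Nor does the protocol say why the two lists differ; the vaccine example illustrates the effect of the difference and is not a documented rationale.
- **That re-entry laboratory tests would be missed because the Section 9.1.4 list is shorter than the Table 2 Re-Entry column.** Footnote 7 to Table 4 already makes the Table 2 re-entry procedures mandatory, and Section 9.1.4 does not claim to be exhaustive. This is not a defect.

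**Conclusion.** The cross-reference in Section 9.1.4 is wrong as written. It contradicts Section 6.1 and the headings of both lists. It replaces a 14-criterion list with a 4-criterion one that omits ten of the 14. Three washouts (8, 9, 10) have no other protection in the protocol, and criteria 11 and 14 have only partial protection.

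The practical consequence is conditional on a site using the cited list despite the headings. Only patients who completed EOS before Amendment 4 and seek re-entry are affected, and the protocol does not give their number. Part C efficacy is summarised descriptively (Section 11.4.3.2) with no formal hypothesis (Section 11.1), and no Part A conclusion is touched. The point should be corrected because it concerns eligibility and safety in children restarting a biologic. It is not a threat to the trial's inference.

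The counts rest on two judgements: that rough counterparts (criteria 2 and 13) count as matched, and that a partial safeguard elsewhere counts as back-up. Stricter readings would raise the numbers; the wrong pointer does not depend on them.

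**What to change.** In Section 9.1.4, change the reference from Section 7.2.2.2 to Section 7.2.2.3. Nothing else needs to change.

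The cost is an editorial correction at the next amendment, with a short memo to sites in the meantime. It adds no criterion and no procedure that the protocol does not already contain.
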